## 1. PURPOSE OF THE STUDY

---

### a. Brief Summary

b. The purpose of this study is to evaluate the effectiveness of different technologies, Virtual Reality and Augmented Reality with modifications as passive content, active content, cognitive load modulation, and positive encouragement coaching to increase the pain threshold as assessed by immersing a hand in ice water.

### c. Rationale for Research in Humans

This study is designed to test the effectiveness of a virtual distraction on healthy volunteers. There is no appropriate substitute for the use of humans in this context, so humans must be used.

---

## 2. STUDY PROCEDURES

---

### a. Procedures

1500 participants (adults, undergraduate, graduate students) recruited by research personal at a booth set up on or near the Stanford University campus. They will have the option of completing the study at the booth, or scheduling an appointment to participate at LPCH at a later time to do all the study. If interested in the study, the research staff will gauge their preferred availability to participate in the study. During the day of their scheduled study appointment, the research assistant will review the study, go over the consent forms, and answer any questions they may have about the study. Exclusion criteria includes (i) patients who do not consent (ii) are currently taking beta blockers or other chronotropic heart medication(s) (iii) have a history of severe motion sickness (iv) currently have nausea (v) currently experiencing seizures (vi) are clinically unstable (vii) have taken pain medications in the last 12 hours Inclusion criteria includes (i) greater than 18 years of age (ii) English speaking (iii) hearing intact

#### PHASE 1

Part 1a: 3 groups of 250 healthy volunteers will be recruited for this 2 part study. Once they consent to participate in the study, the research personnel will do a Sensory perception threshold (time, amplitude) captured via biosensors (Neurometer). Then the first group of 250 participants will be randomized into either control arm (they will not receive any kind of distraction, no technologies) or the use of Virtual Reality. The second group of 250 will be randomized into Active VR, they will play a game or Passive VR, they will be watching a movie in the VR headset. And the third group of 250 will be randomized into Augmented Reality (AR) or VR. The three groups will wait 5 minutes and each participant will switch to the opposite group (i.e. in the first group, VR group will switch to no VR group). Part 1b: Ice bath: Participants immerse hand in ice bath and starting again with their original assigned group (see attached Dahlquist et al., 2007) and keep hand submerged as long as they can withstand the cold or until 4 minutes

have elapsed, whichever comes first. Participants will not be told of the specifics of the time limit, to avoid competitiveness and expectations and will be asked for pain scores every 30 seconds.

## PHASE 2

Once they consent to participate in the study, the research personnel will do a Sensory perception threshold (time, amplitude) captured via biosensors (Neurometer). Part 2a: 250 participants will be recruited and randomized into either VR or VR + Cognitive Load Modulation. Cognitive Load Modulation, increase the intensity of a game to provide more distraction; the game's audio and visuals will intensify, thereby increasing the cognitive load. Ice bath: Participants immerse hand in ice bath and starting again with their original assigned group and keep hand submerged as long as they can withstand the cold or until 4 minutes have elapsed, whichever comes first. They will be asked to inform research staff when they think they can only keep their hand immersed for 5 more seconds at which point the Cognitive Load Modulation (CLM) group will have the virtual experience intensity increased, while the controls will not. Participants will not be told of the specifics of the 4 minute time limit to avoid competitiveness and expectations. Participants will then crossover to the opposite group after a 5 minute rest period.

### Part 2b:

250 participants will be recruited and randomized into either VR or VR with Positive Encouragement Coaching (PEC). One of the research assistants will be encouraging the participants to distract them. Ice bath: Participants immerse hand in ice bath and starting again with their original assigned group and keep hand submerged as long as they can withstand the cold or until 4 minutes have elapsed, whichever comes first. They will be asked to inform research staff when they think they can only keep their hand immersed for 5 more seconds at which point the PEC VR group will have the virtual experience intensity increased, while the controls will not. Participants will not be told of the specifics of the 4 minute time limit to avoid competitiveness and expectations. Participants will then crossover to the opposite group after a 5 minute rest period.

Part 2c: 250 participants will be recruited and randomized into either CLM VR or PEC VR Ice bath: Participants immerse hand in ice bath and starting again with their original assigned group and keep hand submerged as long as they can withstand the cold or until 4 minutes have elapsed, whichever comes first. They will be asked to inform research staff when they think they can only keep their hand immersed for 5 more seconds at which point the PEC VR group and the CLM VR groups will have the virtual experience intensity increased, while the VR only will not. Participants will not be told of the specifics of the 4 minute time limit to avoid competitiveness and expectations. Participants will then crossover to the opposite group after a 5 minute rest period. All the technologies: VR headset/AR headsets have been approved and meet standards established by the Hospital Instrument and Electrical Safety Committee and are currently in use in the perioperative department. All participants will have biometric sensors that will be collecting physiological metrics such as vital signs, heart rate variability, respiratory rate, etc., which will be entered into a REDCap database. The study will be conducted in LPCH and SHC facilities and clinics.

We use a calculator to determine the minimum number of subjects that need to be enrolled in a study in order to have sufficient statistical power to detect a treatment effect. For 2 independent sample study with mean of 7(SD of 1.5) in group 1, mean of 9 in group 2, alpha of 0.05, beta of 0.2 and power of 0.8, 10 patients will be required in each group. To compensate for dropouts and incomplete data, 12 patients are targeted for enrollment in each group. After enrolling the first 24 participants we ran statistics test to calculate the sample size if we want to have sufficient statistical power with the data we collected. The new sample size needs to be 250 participants in each group.

---

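### Parts 2b and 2c give the coaching arm the same intensity increase that defines Cognitive Load Modulation, so neither comparison evaluates coaching as a separate modification

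*Protocol*

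**What the plan says.** The relevant text is in Protocol section 2a (Procedures), Phase 2.

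- **Part 2a** describes CLM as a change to the game: "Cognitive Load Modulation, increase the intensity of a game to provide more distraction; the game's audio and visuals will intensify, thereby increasing the cognitive load". In the ice bath, participants warn staff when they think they can hold on for only 5 more seconds, and at that cue "the Cognitive Load Modulation (CLM) group will have the virtual experience intensity increased, while the controls will not".
- **Part 2b** sets the arms: "250 participants will be recruited and randomized into either VR or VR with Positive Encouragement Coaching (PEC"). Coaching is described as something a person does: "One of the research assistants will be encouraging the participants to distract them". At the same cue, "at which point the PEC VR group will have the virtual experience intensity increased, while the controls will not".
- **Part 2c** (printed below Part 2b) sets the arms: "250 participants will be recruited and randomized into either CLM VR or PEC VR". At the cue, "the PEC VR group and the CLM VR groups will have the virtual experience intensity increased, while the VR only will not".

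The Brief Summary in section 1 and the Background in section 3a list cognitive load modulation and positive encouragement coaching as separate modifications. The SAP specifies outcomes and models for VR versus no VR only. It says nothing about CLM or PEC.

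**The concern.** The description of PEC contains no change to the game, yet the cue instruction for the PEC arm is the Part 2a instruction for CLM with the group name changed. Staff who follow it deliver CLM to the coaching arm.

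Two questions would then go unanswered. Part 2b could not say whether coaching adds anything to VR, because a benefit might come entirely from the intensity increase. Part 2c could not say whether coaching or cognitive load works better, because both arms would receive the cognitive-load component. The VR-only group named in 2c adds to the doubt, since no such arm is randomised there.

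**Working it through.** The plan gives no figure to reproduce on this point. The check is to write down what each arm receives and what each contrast then estimates.

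**Components as written**

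| Part | Arm | Intensity increase at cue | Coaching |
|---|---|---|---|
| 2a | VR | no | no |
| 2a | VR + CLM | yes | no |
| 2b | VR | no | no |
| 2b | VR + PEC | yes | yes |
| 2c | CLM VR | yes | no |
| 2c | PEC VR | yes | yes, if PEC keeps its 2b meaning |

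Across the three parts, no row has coaching without the intensity increase.

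**Contrasts.** On any additive effect scale, let I be the effect of the intensity increase over plain VR, C the effect of coaching over plain VR, and X their interaction when given together.

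| Part | If PEC means coaching only | As written |
|---|---|---|
| 2a: CLM − VR | I | I |
| 2b: PEC − VR | C | I + C + X |
| 2c: PEC − CLM | C − I | (I + C + X) − I = C + X |

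The shift from the intended to the written contrast is the same in both parts:

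- 2b: (I + C + X) − C = I + X
- 2c: (C + X) − (C − I) = I + X

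Both comparisons therefore move by the effect of an intensity increase given on top of coaching. If that increase helps, both move in favour of PEC.

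**Two illustrations, each under a stated assumption**

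- Coaching does nothing (C = 0, X = 0). As written, 2b gives I and 2c gives 0. With coaching only, 2b would give 0 and 2c would give −I. The written design would credit coaching with the full CLM effect and would hide CLM's advantage.
- Both work equally well and do not interact (C = I = d, X = 0). As written, 2b gives 2d and 2c gives d in favour of PEC. With coaching only, 2b would give d and 2c would give 0.

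**Can crossover or analysis repair it?** No. In the crossover each participant has one period per arm, and in the PEC period the two components always come together. Pooling across parts does not help either: 2b minus 2a is (I + C + X) − I = C + X, the same quantity as 2c. C can be separated from X only by assuming that there is no interaction.

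**A stricter reading of 2c.** The Part 2c text does not itself mention coaching. Read on its own, its two arms receive the same thing and differ only in name.

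**Extent.** 250 (2b) + 250 (2c) = 500 of 6 × 250 = 1500 planned participants, or one third. Two of six randomised comparisons are affected.

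**The case against.** The strongest reply is that this is a drafting slip. The 2b cue sentence looks like the 2a sentence with a new group name, and the unexplained VR-only group in 2c also fits carried-over text. The trial may never have been run this way. That is plausible, but it is inference. No other part of the protocol or the SAP corrects the wording, and this is the only instruction on what happens to the PEC arm at the cue. Some staff might follow it and others might not, which would make the arm inconsistent.

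A second reply is that a more intense virtual experience could be loose wording for stepping up the coaching. The protocol gives the phrase no second meaning, and in 2a it is how CLM is delivered.

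A third reply has real force: as written, 2c is still informative. It estimates what coaching adds on top of CLM, so coaching is not wholly inestimable. What is lost is coaching alone against VR, and coaching against CLM. Those are the comparisons that the arm names announce.

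Three limits also stand. The consequences depend on the text being followed literally. The count of 500 shows how many participants are involved and does not measure bias. The VR versus no-VR outcomes in the SAP and Part 2a are untouched.

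**Conclusion.** The concern holds. Followed as written, Part 2b confounds coaching with the intensity increase, and Part 2c is at most an add-on comparison of CLM plus coaching with CLM. Neither answers the question that its arm names pose, although the protocol presents the two modifications as distinct. Both contrasts are displaced by I + X, the effect of the intensity increase when given with coaching. The documents supply no value for that effect, so the displacement cannot be put in seconds or as a hazard ratio.

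The conclusion rests on two readings: that the intensity increase means in 2b and 2c what it means in 2a, and that PEC in 2c includes the coaching described in 2b. If the second fails, 2c compares two identical arms, which is worse. This must be settled before 2b or 2c is run or interpreted.

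**What to change.** 1. Reconcile the description of PEC with the cue instruction in Parts 2b and 2c, and list the components of every Phase 2 arm explicitly, including what happens at the 5-second cue. For coaching and cognitive load to be evaluated separately, the two arms must differ at that cue, and one of them must not contain the other's component.
2. If the intensity increase in the PEC arm is intended, keep it and rename the contrasts: 2b as CLM + PEC versus VR, and 2c as CLM + PEC versus CLM. State that coaching alone is not evaluated.
3. In Part 2c, delete the reference to a VR-only group or say which arm it means, and state whether coaching is given there.

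For parts not yet run, this is a wording amendment with no extra participants, staff or procedures. The SAP is written in the past tense, and the documents do not say whether Phase 2 has taken place. If 2b or 2c has already been run, rewording cannot separate components that were given together. The sponsor should then establish from study records what the PEC arm received and label the results accordingly.

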## **b. Procedure Risks**

Using AR/VR carries minimal risk. The main risk is developing nausea and/or dizziness, which will be monitored for and can be easily treated by removing the headset. Ice bath protocols have been performed for decades and we will adhere to safety standards set by these protocols such as constant monitoring of ice bath temperature via thermometer, hard time limit, rest period between phases, and heart rate monitoring via pulse oximeter.

---

**c. Use of Deception in the Study**

NA

---

**d. Use of Audio and Video Recordings**

NA

---

**e. Alternative Procedures or Courses of Treatment**

This does not involve specific treatments. No standard treatment will be withheld, the alternative to this study is for the participant not to engage in our research study.

---

**f. Will it be possible to continue the more (most) appropriate therapy for the participant(s) after the conclusion of the study?**

Yes - VR/AR technologies described here are currently in use for the entire hospital.

---

**g. Study Endpoint(s)**

The endpoint of the study will be determined by the completion of the target number of participants. The target number of participants 1500.

---

**3. BACKGROUND**

---

**b. Findings from Past Animal Experiments**

**4. DEVICES USED IN THE STUDY**

**a. Investigational Devices (Including Commercial Devices Used Off-Label)**

Investigational Device 1	
Name:	Virtual Reality Headset-Gear VR
Description:	Portable VR headset to display a passive relaxing experience such as sitting on beach or exploring the ocean by looking around. The active experience may include playing a game to collect bananas as monkey, flying a paper airplane, or catching balls in a basket.
Significant Risk? (Y/N)	N
Rationale for Non-Significant Risk	VR headsets are commercially available devices for gaming and relaxation with insignificant risks. The possible side effects are nausea and dizziness, they can be solve with removing the headset.

**5. PARTICIPANT POPULATION**

**a. Planned Enrollment**

- (i) 1500 participants will be enrolled during our study
- (ii) Students, adults, visitors and personnel working or volunteering at LPCH or SHC facilities
- (iii) These participants are being chosen because we are focusing on a low risk population

**b. Age, Gender, and Ethnic Background**

Patients 18 and older of mixed genders and ethnic backgrounds.

**c. Vulnerable Populations**

Up to 1500 healthy volunteers, students, adults, visitors and personnel working or volunteering at LPCH or SHC facilities could potentially be enrolled in this study. This is necessary as this study aims to investigate the effectiveness of non-invasive technologies (AR/VR/Tablet) with modifications at altering pain tolerance. . Although we expect minimal risks in this study, there may be a chance of patients experiencing intolerable symptoms such as dizziness and nausea from VR/AR use. In such case our health care providers will be notified and appropriate measures will be taken to ensure patient safety. The risk discovery of an individual's participation is mitigated by our measures to keep patients data de-identified and stored in a secure and encrypted database.

---

**d. Rationale for Exclusion of Certain Populations**

NA

---

**e. Stanford Populations**

Up to 1500 volunteers could be enrolled in the study.

---

**f. Healthy Volunteers**

NA

---

**g. Recruitment Details**

School of Medicine research assistants who are not affiliated with the volunteers in any way, will recruit via an informational booth set up on the Stanford Campus after receiving University approval and at LPCH. At the booth and at LPCH some research assistant will be running the study and other research assistants will be around to booth to inform the people about the study. The research assistants will not coerce or influence an volunteer's decision to participate. If volunteer declines interest, research personnel will respect their decision and will not pursue them for any further involvement in this study.

---

**h. Eligibility Criteria**

i. Inclusion Criteria

(i) greater than 18 years of age (ii) English speaking (iii) hearing intact

ii. Exclusion Criteria

- (i) patients who do not consent
  - (ii) are currently taking beta blockers or other chronotropic heart medication(s)
  - (iii) have a history of severe motion sickness
  - (iv) currently have nausea
  - (v) currently experiencing seizures
  - (vi) are clinically unstable
- 

**i. Screening Procedures**

No PHI will be collected prior to enrollment. If the participant expresses interest they will be approached by a research assistant. If they decline they will not receive any further information about the study. If the participant expresses interest, the RA will proceed with the consent and appropriate stage placement, randomization will occur for the second phase (either standard of care of VR/AR/table simulation) If the potential candidate declines interest, we will respect their decision and will not pursue them for any further involvement in this study. Only authorized members of the study team will have access to patient information.

---

**j. Participation in Multiple Protocols**

Participants will be asked if they are participating or intend to enroll in other studies. Participants will be allowed to participate in more than one study if it can be determined that this poses no increased risk to the

participants or the integrity of the data collected for either study.

---

**k. Payments to Participants**

Participants will receive a \$5.00 gift card for participation in this study.

---

**l. Costs to Participants**

NA

---

**m. Planned Duration of the Study**

- i) Screening per patient will take approximately 10-15 minutes.
- ii) Active participation for the participant will last the duration of the procedure, we estimate about 1 hour, from the time of consent to the debrief.
- iii) The analysis of the data will take approximately 1-2 years.

---

**6. RISKS**

---

**a. Potential Risks**

i. Investigational devices

VR and AR headset and software- we expect a low incidence of intolerability (primarily nausea and dizziness) in less than 5% of all cases, in which case VR headset can simply be removed and any follow-up care can be assessed by the healthcare provider.

ii. Investigational drugs

NA

iii. Commercially available drugs, biologics, reagents or chemicals

NA

iv. Procedures

The VR and AR headsets unit will be placed on patients by trained staff and will have minimal risk to the patient. VR and AR headsets will be set up by trained study staff. All devices are wiped with hospital grade disinfection wipes according to hospital protocols. All devices are compliant with infection control standards at LPCH and hospital instrument and electrical compliance.

v. Radioisotopes/radiation-producing machines

NA

vi. Physical well-being

NA

vii. Psychological well-being

NA

viii. Economic well-being

NA

ix. Social well-being

NA

x. Overall evaluation of risk

NA

---

**b. International Research Risk Procedures**

NA

---

**c. Procedures to Minimize Risk**

Participants/patients will be informed that they may withdraw from the study at any time, for any reason, with no consequences for withdrawing, and the standard clinical care and procedures for their care will continue as normal. All data will be de-identified and stored in a secure, encrypted database for clinical analysis.

---

**d. Study Conclusion**

The experiment will terminate at the conclusion or enrollment. There is no anticipated interim analysis, and no reason to consider early termination based on the low level of risk associated with this study. If the patient decides that he/she does not want to participate in the study at any time, we will terminate the study.

---

**e. Data Safety Monitoring Plan (DSMC)**

i. Data and/or events subject to review

NA

ii. Person(s) responsible for Data and Safety Monitoring

NA

iii. Frequency of DSMB meetings

NA

iv. Specific triggers or stopping rules

NA

v. DSMB Reporting

NA

vi. Will the Protocol Director be the only monitoring entity? (Y/N)

NA

- vii. Will a board, committee, or safety monitor be responsible for study monitoring?  
(Y/N)

NA

---

**f. Risks to Special Populations**

NA

---

**7. BENEFITS**

It is unknown if participants enrolled in the study will directly benefit, but we anticipate that the technology-based distractions have great potential to be used in future medical encounters.

---

**8. PRIVACY AND CONFIDENTIALITY**

All participant information and specimens are handled in compliance with the Health Insurance Portability and Accountability Act (HIPAA) and privacy policies of Stanford University, Stanford Health Care, and Stanford Children's Health.

Evaluating the Effectiveness of Immersive Technologies, Virtual Reality and Augmented Reality, to Increase Pain Threshold During Ice Immersion

NCT04196686
February 23, 2022

[name], Principal Investigator
Stanford University
Stanford, California 94305

Statistical Analysis Plan

Outcomes

The primary outcome was Virtual Reality (VR)'s effect on pain tolerance. The first secondary outcome was VR's effect on perceived pain intensity. Our final secondary outcome was to investigate the effects of VR on modulating sympathetic response in the presence of painful stimuli. We made no changes to trial outcomes after the trial commenced.

Measures

We assessed pain tolerance by measuring the duration that participants kept their hand immersed within the ice bath (in seconds). Given that the cold pressor test produces an uncomfortable experience, we considered longer duration within the ice bath to represent increased pain tolerance.

Our first secondary outcome, VR's effect on perceived pain intensity, was assessed by collecting pain scores from participants every 30 seconds while their hands were immersed. We measured pain scores on a 0-10 scale, where 0 represented no pain and 10 represented the most excruciating pain imaginable.¹

Our final secondary outcome, the effects of VR on modulating sympathetic response in the presence of painful stimuli, was assessed by analyzing SCRD (in microsiemens) per 30 second interval. We refer to each of these 30 second intervals as a separate epoch. Skin conductance is expected to increase with increasing sympathetic nervous system activity, as sympathetic activity increases sweat secretion to increase skin conductance.

Sample Size

We considered a hazard ratio of 0.6 to be clinically significant given that it would indicate an approximate 30% improvement in pain tolerance. Assuming an alpha of 0.05 and power of 80%, sample sizes of 30 people in the VR group and 59 people in the control group were needed to be adequately powered to an estimated hazard ratio of 0.6.

Randomization

We randomized participants to their first ice immersion intervention (VR or no VR) and hand use (dominant or non-dominant) using an electronic random number generator with a 1:1 allocation.² Participants then crossed over for their second ice immersion

Statistical Methods

To analyze the effectiveness of VR on pain tolerance, we analyzed the survival time using a Cox mixed-effect model with trials nested in subject and fit using the coxme package using R software. We controlled for dominant hand treatment assignment, dominant hand order, and gender.

To analyze our secondary outcomes, we used linear mixed effects models with outcomes nested in subject using the lme4 package in R. We controlled for dominant hand treatment assignment, dominant hand order, and gender when analyzing pain perception. The variables in the physiologic model were SCRD change over time and the SCRD change between groups, defined as those with and without VR.

References

- [2] Suresh K. An overview of randomization techniques: An unbiased assessment of outcome in clinical research. *J Hum Reprod Sci*. 2011;4(1):8-11.

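### Pain is scored only while the hand stays in the bath, so the pain comparison is cut off by the primary outcome and may be biased, plausibly toward the null

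*SAP*

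**What the plan says.** - **Scoring.** SAP, Measures: perceived pain intensity is obtained by "collecting pain scores from participants every 30 seconds while their hands were immersed", on a 0-10 scale. Protocol section 2a, Phase 1, Part 1b agrees: participants "will be asked for pain scores every 30 seconds". Neither document states when the first score is taken, or describes a score at 0 s or at hand removal.
- **Withdrawal.** Protocol section 2a: participants "keep hand submerged as long as they can withstand the cold or until 4 minutes" have passed. With a 240 s limit and 30 s spacing, an immersion can give at most 240/30 = 8 scores.
- **Meaning of duration.** SAP, Measures: "we considered longer duration within the ice bath to represent increased pain tolerance". Duration is the primary outcome.
- **Expected VR effect on withdrawal.** SAP, Sample Size: "We considered a hazard ratio of 0.6 to be clinically significant".
- **Pain analysis.** SAP, Statistical Methods: "we used linear mixed effects models with outcomes nested in subject using the lme4 package in R". The listed adjustments for pain are two hand-dominance variables and gender. Time is named for the skin-conductance model but not for the pain model.
- **Missing scores.** Neither document gives a rule for an immersion without a score, or a sensitivity analysis for scores cut off by withdrawal.

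**The concern.** The variable that VR is meant to change decides which pain scores are seen. Three consequences follow.

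1. If the first score is at 30 s, an immersion that ends sooner gives none. If VR prolongs immersion, this happens more often without VR.
2. Any later withdrawal leaves unrecorded the pain that prompted it.
3. Longer VR immersions contribute more late scores. With no time term, any trend of pain over the immersion is partly attributed to VR.

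At stake is the estimate of the VR effect on pain intensity. It could be shrunk, or under some pain courses enlarged, by the trial's own primary effect.

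**Working it through.** **Plan's own figure.** The SAP gives no figure for missing pain scores. The only planning value used here is the hazard ratio of 0.6. The sample size attached to it (30 + 59 = 89) does not reproduce with the standard two-sided Schoenfeld formula for independent groups: (1.960 + 0.842)² / (0.25 × (ln 0.6)²) gives 121 events at 1:1, and 135 at 30:59. Nothing below depends on that.

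**Step 1: immersions with no score.** Let p be the share leaving before 30 s without VR (assumed, as the documents give none). Under proportional hazards the share with VR is 1 − (1 − p)^0.6.

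| Without VR (assumed) | With VR | Gap, points |
|---|---|---|
| 5% | 3.0% | 2.0 |
| 10% | 6.1% | 3.9 |
| 20% | 12.5% | 7.5 |
| 30% | 19.3% | 10.7 |

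**Step 2: effect on the pain estimate.** The crossover was simulated with 300 people and 60 runs per scenario (simulation SE about 0.01-0.02). Each person has one VR and one no-VR immersion, with scores at 30 to 240 s while immersed. Assumed values are:
- a true VR effect on pain of −1.0 and a hazard ratio of 0.6;
- pain SDs of 1.5 (person), 1.0 (immersion) and 0.8 (residual);
- a log hazard rising by 0.5 per point of person-level or immersion-level pain, where such a link is present.

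Each cell gives the random-intercept estimate at baseline p = 5% / 15% / 30%.

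| Withdrawal depends on | Flat pain, no time term | Pain +0.3 per 30 s, no time term | Same, time added | Pain −0.2 per 30 s, no time term | Same, time added |
|---|---|---|---|---|---|
| VR only | −0.97 / −1.00 / −0.98 | −0.95 / −0.91 / −0.85 | −0.99 / −1.02 / −1.02 | −1.02 / −1.07 / −1.11 | −0.99 / −0.99 / −0.99 |
| Stable personal sensitivity | −1.01 / −1.02 / −1.01 | −0.95 / −0.89 / −0.86 | −1.00 / −0.98 / −0.99 | −1.04 / −1.05 / −1.05 | −1.02 / −0.99 / −0.97 |
| Immersion-specific pain | −0.96 / −0.88 / −0.88 | −0.91 / −0.85 / −0.73 | −0.95 / −0.94 / −0.85 | −0.99 / −0.97 / −0.99 | −0.97 / −0.90 / −0.87 |
| Both | −0.95 / −0.92 / −0.90 | −0.92 / −0.86 / −0.80 | −0.96 / −0.93 / −0.89 | −1.02 / −1.00 / −0.97 | −0.99 / −0.94 / −0.88 |

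**Reading the table.**
- With flat pain, the first two rows show essentially no bias.
- Immersion-specific pain gives 4-12% attenuation with flat pain, and 3-15% when pain has a trend and time is modelled.
- Rising pain with time omitted takes the estimate as far as −0.73, or 27% toward zero. A second simulation of the same design gave up to about 21%, and about 5-15% for immersion-specific pain.
- Falling pain with time omitted takes it as far as −1.11, or 11% away from zero.
- A time term removes the part due to the pain trend. It does not remove the part due to immersion-specific withdrawal.

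**The case against.** The strongest reply is that the design already protects the comparison. Everyone has both conditions and outcomes are nested in subject, so a person who leaves one immersion early usually still contributes scores in the other. For withdrawals after 30 s, a likelihood model with time uses the scores already given. Much of this stands: with flat pain, stable sensitivity alone produces no material bias in the table.

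It also stands that early withdrawal may be rare. In a separate simulation of the 30 s score alone, attenuation was about 1-4% when 1% of control immersions ended early and 3-9% when 5% did.

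A reader might infer more: that the comparison necessarily understates VR whenever VR works, by something like 13-30%. The documents do not support that. Figures of this size came from simulations of the 30 s score alone, with 10-30% early control withdrawal and pain tied to tolerance in that same immersion (10-34%). When the tie ran only through the person, the result was 4-11%. The SAP's analysis uses up to eight scores per immersion, and with falling pain the bias can go the other way. Two further premises are also unconfirmed: that no score was taken at 0 s or at withdrawal, and that early withdrawal is in fact more common without VR, which is the trial's hypothesis.

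The reply does not remove the gap. Withdrawal driven by pain in that immersion is plausible, since people leave when they can no longer bear it. The nested model does not correct for that, and the listed pain model has no time term.

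**Conclusion.** The concern holds as a risk of bias in the first secondary outcome, not as a demonstrated understatement. Pain scores are cut off by the primary outcome, with no withdrawal score, no rule for unscored immersions and no listed time term. The likely direction is toward the null. The size runs from nil (stable sensitivity only, flat pain), through about 5-15% (immersion-specific pain), to about 20-27% (pain also rising and time omitted), with about 11% away from the null possible if pain falls. The unequal loss of immersions assumes a first score at 30 s and a hazard ratio of 0.6. The bias figures also assume the withdrawal rates, pain courses and variance components listed in the working. If almost nobody leaves before 30 s, the early-loss part is negligible. Later cut-off and the missing time term would still need attention.

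**What to change.** **For all data, including data already collected:**
- Add time in the bath (30 s epoch) to the pain mixed model.
- Report the number of immersions with no score, by condition. Durations are already recorded for the primary outcome.
- State when the first score was taken, and whether any was taken at withdrawal.
- Run a sensitivity analysis: either a matched time-point comparison, using only times at which both of a person's immersions have a score, or a joint model of pain and withdrawal. The first removes unequal timing but still selects immersions that lasted. The second addresses that selection under its own model assumptions.
- Do not treat a worst rank for early leavers as evidence on pain intensity. If VR only lengthened immersion and left pain unchanged, the no-VR condition would collect more worst ranks and VR would appear to reduce pain.

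**For immersions still to be run:** ask for one more 0-10 score at hand removal and record its time. Pre-specify the score at the earlier of 30 s or withdrawal as a supporting early comparison. In simulation this moved the estimate closer to the truth in most of the biased scenarios.

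**Cost:** one verbal question per immersion, a short SAP addition and some analysis time. The withdrawal score falls at a different time in each immersion, so it must be analysed with its time. It cannot be added to completed immersions, and the SAP's past tense suggests that many or all of those it reports are complete.
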